## **5.9 Other Analyses**

### **5.9.1 Pressure Pain Threshold**

Pressure pain threshold will be assessed by pressure algometry. Pressure algometry will be performed at 2 sites on the body: (1) the lateral forearm and (2) the contralateral anterior thigh. Triplicate and average PPT scores by time points will be listed for all study participant at each time point. Mean and change from Baseline in average PPT score will be summarized by assessment site, treatment sequence and period, based on the FAS. If only one or two PPT assessments are collected at a time point, the available assessments will be used for the average PPT score at that time point.

## **5.10 Biomarkers**

Venous blood samples will be collected to measure IgG binding as an exploratory endpoint.

The reporting and analysis of the exploratory biomarker results will be conducted separately from the CSR and will not be covered in this SAP or associated TFL shells.

## **5.11 Immunological Endpoint**

The following blood samples for immunological testing will be collected as specified in the protocol schedule of activities:

- IgA, IgE, IgM (for participants randomized under Protocol Amendments 1 and 2 only)
- Serum complement (C3, C4)
- Plasma complement (C3a, C5a)

A listing of serum immunoglobulin laboratory results will be provided using the SS-r.

Serum and plasma complement results collected at Baseline and at any post-Baseline visits, will be listed using SS-r.

## **5.12 Early readout analysis and data monitoring**

### **5.12.1 Early Readout Analysis**

An Early Readout Analysis is planned to be conducted after all randomized study participants have either completed the BPI-SF assessment at Visit 27, or have withdrawn from the study.

For this Early Readout Analysis, a snapshot of the database will be taken once the BPI-SF data has been entered at Visit 27 (or earlier in the case of withdrawals) for the final randomized participant. The data will be cleaned for the purpose of the analysis. Details regarding the unblinding of individual team members and results dissemination will be provided in a separate unblinding plan. The study team will be unblinded following data cleaning and all study data, including the live random code and any vendor data previously considered unblinding will be provided. Some study team members will remain blinded until database lock. Details of team members who should remain blinded are provided in the unblinding plan. The Investigators and study participants will remain blind to the assigned treatment dosing regimen until the Follow-Up Period is complete and the database is locked.

A subset of key TFLs will be provided which will include the evaluation of the primary efficacy estimand, the secondary efficacy endpoints, PK and PD data, as described in [Section 5.8.2](#), [Section 5.8.4](#), [Section 5.9.1](#) and [Section 5.5](#).

### **5.12.2 Data Monitoring**

A SMC will regularly review (approximately every 3 months, with the option to adapt the frequency based on recruitment rates) the available blinded safety data. The first SMC review will be conducted approximately 2 months after randomization of the first study participant, or when 25% of the study participants are randomized, whatever comes first. The SMC will decide if the study is safe to continue. Details will be described in a separate charter.

If there are safety concerns during the SMC session an ad hoc closed SMC meeting may be called if revealing treatment allocation would aid decision making. The members of closed SMC sessions will be restricted and specified in the charter.

## **6 CTR AND DSUR OUTPUTS**

### **6.1 CTR**

The following tables outlined in previous SAP sections fulfil the criteria for transparency reporting for clinicaltrials.gov and EudraCT:

- DS\_T\_03 Disposition and Discontinuation Reasons [RS] as per [Section 5.2.1](#)
- DM\_T\_01 Demographics (all age categories are mandatory) [RS] as per [Section 5.3.1](#)
- AE\_T\_01 Incidence of TEAEs – Overview (mandatory, including both All Deaths and TEAE leading to Deaths) [SS-t] as per [Section 5.6.2](#)

- AE\_T\_06 Incidence of Non-Serious TEAEs Above Reporting Threshold of 5% of participants [SS-t] as per [Section 5.6.2](#)
- DS\_T\_04 Discontinuation due to AEs [RS] as per [Section 5.2.1](#)
- AE\_T\_04b Incidence of serious TEAEs by Relationship [SS-t]
- AE\_T\_04b Incidence of fatal TEAEs by Relationship [SS-t]

For results disclosure on public registries (eg. ClinicalTrials.gov), treatment-emergent adverse events and treatment-emergent serious adverse events will be published.

## 6.2 DSUR

The following tables will be created by the UCB statistical programming team for reporting for DSUR:

- EX\_T\_03 Cumulative Duration of Exposure. This table will be created for DSUR outputs needed whilst the study is ongoing and also once the study is completed.
- EX\_T\_03 Cumulative Duration of Exposure by Treatment, Age Group and Gender. This table will be created once the study is completed.
  - EX\_T\_03 Cumulative Duration of Exposure by Treatment and Race. This table will be created once the study is completed.

## 8 APPENDICES

### 8.1 Appendix 1: Abnormality Criteria for Laboratory and Vital Sign Parameters

#### 8.1.1 Laboratory Assessments Marked Abnormality Criteria

The following criteria will be applied in the determination of marked abnormalities for laboratory assessment values. They are based on Version 5 of the Common Terminology Criteria for Adverse Events (CTCAE) grade 3 or higher criteria. If both high and low criteria are shown for a parameter, the criteria should be summarized separately in tabular or graphical data summaries. A treatment-emergent markedly abnormal assessment is defined as any abnormal assessment obtained on or after the first dose of IMP in Run-In, and on or before the earliest of the following: the last date of infusion (including Run-Out, if applicable) +56 days, final contact date or death and where the corresponding Baseline value does not meet the criteria.

#### Hematology

PARAMETER	UNIT (conventional)	UNIT (standard)	MARKED ABNORMALITY CRITERIA
Hemoglobin	g/dL	g/L	<8.0 g/dL; <80 g/L
WBC (Leukocytes) 	10  /L	10  /L	Low: <2.0 x 10  /L
			High: >30 x 10  /L
Lymphocytes Absolute	10  /L	10  /L	Low: <0.5 x 10  /L
			High: >20 x 10  /L
Neutrophils Absolute	10  /L	10  /L	<1.0 x 10  /L
Platelets	10  /L	10  /L	<50.0 x 10  /L

#### Chemistry

PARAMETER	UNIT (conventional)	UNIT (standard)	MARKED ABNORMALITY CRITERIA
AST (SGOT)	U/L	U/L	>5.0 x ULN
ALT (SGPT)	U/L	U/L	>5.0 x ULN
ALP (Alkaline Phosphatase)	U/L	U/L	>5.0 x ULN
Bilirubin (Total)	mg/dL	umol/L	>3.0 x ULN if Baseline value is normal (based on reference range); >3.0 x Baseline value if Baseline is abnormal
Albumin 	g/dL	g/L	<2 g/dL; <20 g/L
Creatinine	mg/dL	umol/L	>3.0 x ULN or >3.0 x  Baseline
Estimated glomerular filtrate rate (eGFR)	mL/min/1.73 m 	mL/min/1.73 m 	eGFR ≤29 mL/min/1.73 m 

PARAMETER	UNIT (conventional)	UNIT (standard)	MARKED ABNORMALITY CRITERIA
C reactive protein (CRP) 	mg/L	mg/L	>10 mg/dL; >100mg/L
Calcium	mg/dL	mmol/L	Low: Corrected serum calcium of <7.0 mg/dL; <1.75 mmol/L
			High: Corrected serum calcium of >12.5 mg/dL; >3.1 mmol/L
Immunoglobulin G	(g/L)	(g/L)	<1.09 g/L (BLQ)
Potassium	mmol/L	mmol/L	Low: <3.0 mmol/L
			High: >6.0 mmol/L
Sodium	mmol/L	mmol/L	Low: <125 mmol/L
			High: >155 mmol/L
Glucose 	mg/dL	mmol/L	Low: <40 mg/dL; <2.2 mmol/L
			High: > 250 mg/dL; >13.9 mmol/L
Total Cholesterol	mg/dL	mmol/L	>400 /dL; >10.34 mmol/L
Triglycerides	mg/dL	mmol/L	>500 mg/dL; >5.7 mmol/L

Abbreviations: ALT= alanine aminotransferase; AST = aspartate aminotransferase; dL = deciliter; GGT: gamma-glutamyltransferase; L = liter; mg = milligram; mmol = millimoles;  $\mu$ g = microgram; U = unit; ULN = upper limit of normal

Note: Marked abnormality criteria are defined by Grade 3 or higher events according to the Common Terminology for Adverse Events (CTCAE), Version 5.0, November 17, 2017 unless otherwise noted.

WBC (Leukocytes) markedly abnormal high criterion is not based on Version 5 CTCAE Grade 3 or higher criteria. Due to the allowance of concomitant steroid medication that by its mechanism of action may elevate WBCs, the safety alert is related to infection risk which would be identified by a lower cut-point than the standard which is related to acute leukemias. A markedly abnormal high cut-point  $>30 \times 10^9/L$  is applied to flag leukocytosis (George 2012).

Albumin data is classed as unblinding and results will therefore only be available after unblinding.

Includes CRP and High Sensitivity (HS) CRP. Reference for marked abnormality criteria: Nehring, S.M.; Goyal, A.; Patel, B.C. (2020). StatPearls Publishing, web link: <https://www.ncbi.nlm.nih.gov/books/NBK441843/>.

Glucose high criterion defined by Grade 3 and higher events according to CTCAE, Version 4.03, June 14, 2010.

### 8.1.2 Vital signs

Abnormality criteria to be applied in the assessment of vital signs parameter values are given below. A treatment-emergent markedly abnormal assessment is defined as any abnormal assessment obtained on or after the first dose of IMP in Run-In, and on or before the earliest of the following; the last date of infusion (including Run-Out, if applicable) +56 days, final contact date or death and where the corresponding Baseline value does not meet the criteria.

PARAMETER	ABNORMALITY CRITERIA
Pulse Rate (beats/minute)	$\leq 50$ and a decrease from Baseline of $\geq 15$ $\geq 120$ and an increase from Baseline of $\geq 15$
Systolic Blood Pressure (mmHg)	$\leq 90$ and a decrease from Baseline of $\geq 20$ $\geq 180$ and an increase from Baseline of $\geq 20$
Diastolic Blood Pressure (mmHg)	$\leq 50$ and a decrease from Baseline of $\geq 15$ $\geq 105$ and an increase from Baseline of $\geq 15$
Temperature	$>38.3^{\circ}\text{C}$
Body Weight	$\geq 10\%$ decrease from Baseline $\geq 10\%$ increase from Baseline

## 8.2 Appendix 2: Handling of Dates

Partial or completely missing dates may be imputed for the following reasons:

- Classification of AEs as TEAEs
- Durations of AEs
- Classification of medications and medical procedures as prior or concomitant
- Time since diagnosis of FMS and time since first symptoms of FMS.

Imputed dates will not be shown in the listings; all dates will be displayed as reported in the database.

### 8.2.1 Adverse Events

For the classification of TEAEs, the rules below will be applied for partial or completely missing start dates. In general dates will be imputed conservatively such that if possible an AE will be classified as treatment-emergent. If a TEAE could potentially be assigned to more than one period, based on imputation, the following priority order will be used to impute the dates – Treatment Period 2>Treatment Period 1>Run-In Period:

- If only day is missing:
  - If month and year are the same as the first dose in Treatment Period 2, then use the date of first dose in Treatment Period 2, else;
  - If month and year are the same as the first dose in Treatment Period 1, then use the date of first dose in Treatment Period 1, else;
  - If month and year are the same as the first dose in Run-In (and not the same as the first dose in Treatment Period 1), then use the date of first dose in Run-In.
  - If none of the above apply then use the 1st of the known month or the date of Screening if this is later.

If any of the above result in an imputed start date after a known end date then use the 1st of the start month or the date of Screening if this is later.

- If day and month are missing:

- If the year is the same as the first dose in Treatment Period 2, then use the date of first dose in Treatment Period 2, else;
- If the year is the same as the first dose in Treatment Period 1, then use the date of first dose in Treatment Period 1, else;
- If the year is the same as the first dose in Run-In (and not the same as the first dose in Treatment Period 1 or Treatment Period 2), then use the date of first dose in Run-In.
- If none of the above apply then use the 1st of January in the known year or the date of Screening if this is later.

If any of the above result in an imputed start date after a known end date then use the 1st of January in the known year or the date of Screening if this is later.

- If the start date is completely unknown, then use the date of first dose in Treatment Period 2. If this results in an imputed start date that is after a known end date, then use
  - The date of first dose in Treatment Period 1 (if prior to known end date), else;
  - The date of first dose in Run-In (if prior to known end date), else;
  - 1st of January in the year of the end date or the date of Screening if this is later.

Missing or partially missing dates will be imputed as described in the below table for the calculation of duration of each AE. Adverse event duration is computed in and reported in days.

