### **5.6.2 Adverse Events**

All AEs will be coded using MedDRA® and characterized as pre-treatment and treatment-emergent according to the intake of each treatment. Adverse events with a start date prior to the first dose of IMP in the Run-In Period will be defined as pre-treatment AEs. A TEAE is defined as any AE with a start date on or after the first dose of IMP in Run-In, and on or before the earliest of the following: the last date of infusion (including Run-Out, if applicable) +56 days, final contact date or death. A TEAE is also defined as any unresolved event already present before administration of treatment that worsens in intensity following exposure to the treatment.

Adverse events will be summarized by treatment period and treatment group based on the SS-t. If a participant receives an incorrect treatment per the randomization schedule, the participant will be excluded from the summaries, and the AEs for this participant will be listed only. In such cases these will be noted in the footnotes for the relevant tables. Pre-treatment AEs will not be included in any summaries.

Adverse events will be assigned to the respective treatment period and treatment group based on the start date of the AE. The assignment of AEs to a given treatment period is summarized in Appendix 4 Section 8.4. The treatment groups will be summarized per treatment period in the following way:

- Run-In:
  - PBO (All 3 sequences)
- Treatment Period 1
  - RLZ (Sequence 1)
  - Pooled PBO (Sequence 2 and 3)
- Treatment Period 2

---

- RLZ/RLZ (Sequence 1)
- PBO/RLZ (Sequence 2)
- PBO/PBO (Sequence 3)
- Run-Out and SFU (pooled)
  - RLZ/RLZ (Sequence 1)
  - PBO/RLZ (Sequence 2)
  - PBO/PBO (Sequence 3)

The total N within the summary tables will correspond to the number of participants randomized to the respective treatment sequence who receive at least one dose of IMP in the given treatment period or who entered the SFU period.

For details regarding partial dates, see Appendix 2 [Section 8.2](#).

The number and percentage of participants who experience TEAEs will be summarized by MedDRA™ SOC, HLT, and PT as described above.

Summaries of TEAEs will include the following:

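### When only the year of an AE's start is known, the SAP 8.2.1 fallback skips the Period 1 and Run-In dates, so an AE that could have started on treatment can be classed as pre-treatment

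*SAP*

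**What the plan says.** SAP 8.2.1 opens with a principle: "In general dates will be imputed conservatively such that if possible an AE will be classified as treatment-emergent". If an event could fall in more than one period, "the following priority order will be used to impute the dates – Treatment Period 2>Treatment Period 1>Run-In Period". Three cases follow.

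- **Day and month missing.** The opening step reads: "If the year is the same as the first dose in Treatment Period 2, then use the date of first dose in Treatment Period 2," otherwise Period 1 if its year matches, otherwise Run-In. A closing sentence deals with conflicts and begins: "If any of the above result in an imputed start date after a known end date then use the". The fallback that it names is the first day "of January in the known year or the date of Screening if this is later".
- **Only the day missing.** The same structure by month, with the 1st of the start month (or Screening if later) as the fallback. The words of the closing sentence quoted above occur in both cases.
- **Start completely unknown.** The Period 2 first-dose date is used. If it is after a known end date, the rule steps down to Period 1: "The date of first dose in Treatment Period 1 (if prior to known end date), else". Run-In is tried next: "The date of first dose in Run-In (if prior to known end date), else". Only then does it turn to 1 January of the end year or Screening.

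SAP 5.6.2 classes an AE starting before the first Run-In dose as pre-treatment and adds: "Pre-treatment AEs will not be included in any summaries". SAP 8.4.1 assigns periods after imputation.

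**The concern.** The same problem, an imputed start later than the known end, is solved in two ways within one section. With no start date at all, the plan works back through Period 1 and Run-In, as its priority order requires. With the year known, it makes one attempt and then moves to a date that usually precedes the first dose. Knowing more about the start therefore gives the less conservative classification, against the stated principle, and no reason is offered.

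Occurrence of TEAEs is a secondary endpoint (SAP Table 1-1). An affected event drops out of the TEAE tables (5.6.2), the adverse-events-of-focus tables (5.6.5) and the TEAE tables by ADA category (5.7). It could be an event on rozanolixizumab in Sequence 1, Period 1. Its computed duration also grows, because SAP 8.2.1 measures duration from the imputed start.

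**Working it through.** The documents give no figure to reproduce, so the check applies the rules literally to the SAP's own schedule.

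**Inputs** (SAP 5.1.1.2): Screening Day -42 (the full 28 days), first Run-In dose Day -14, first Period 1 dose Day 1, first Period 2 dose Day 85. An imputed start before the first Run-In dose is pre-treatment (SAP 5.6.2).

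**Worked example.** Day 1 is 14 March 2024, so Screening is 1 February, Run-In 29 February and Period 2 6 June. The AE start is recorded as 2024 and the end as 20 May 2024.

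| Rule | Imputed start | Class | Duration (end − start + 1) |
|---|---|---|---|
| Year-only, as written | 6 June is after 20 May, so the later of 1 January and 1 February = 1 February | Pre-treatment | 110 days |
| Completely unknown | 6 June fails; 14 March is before 20 May | TEAE, Period 1 | 68 days |
| Year-only, participant left before Period 2 | No Period 2 date to match, so 14 March | TEAE, Period 1 | 68 days |

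The last row shows that the class depends on whether the participant later continued.

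**Conditions needed for loss of TEAE status.** (a) Only the year of onset is known. (b) A Period 2 dose was given in that year. (c) The end date is known and precedes that dose. (d) The first Run-In dose was after 1 January of that year. If (d) fails, the fallback of 1 January is on or after the first Run-In dose and the event stays a TEAE, possibly in the wrong period.

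**Enumeration.** Assumptions: Day 1 on each of 365 dates (2023); onset every third day of Period 1; duration 3, 7 or 14 days; end before Period 2. The allowed onsets number 27, 26 and 24, so the cases number 365 × (27 + 26 + 24) = 28,105.

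- Year-only rule: 20,482 pre-treatment (20,482 / 28,105 = 72.9%), 6,545 kept in Period 1 (23.3%), 1,078 kept but placed in Run-In (3.8%).
- Unknown-date rule: 0 pre-treatment.
- Year-only rule with no Period 2 dose: 0 pre-treatment.

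**Day-missing rule.** Here I took every onset from the first Run-In dose to Day 84, again ending before Period 2. The share classed pre-treatment is 7.2% for same-day events, 5.9% for 3 days, 3.9% for 7 days and 0% for 14 and 28 days. All of these had onset in Run-In and ended before the first Period 1 dose. This follows from the rule: the fallback can precede the first Run-In dose only when Run-In and Period 1 start in the same month and the event ended before Period 1. Periods 1 and 2 start 84 days apart and never share a month.

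**After the change below.** Over the same onsets and durations of 0, 3, 7, 14 and 28 days, both partial-date rules class 0% as pre-treatment. The unknown-date rule as written leaves one small gap: an event starting and ending on the first Run-In dose date fails its strictly-before test. That is 1 onset day in 98, or 1.0% of same-day events.

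**The case against.** The best counter-argument is rarity. AE review takes place at every visit and treatment-period visits are weekly, ±2 days (Protocol 1.3). A site that records an end date will normally know at least the onset month. No affected case is shown to exist. This stands, and it limits the practical weight of the point.

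The event is also not lost from the report. SAP 5.6.2 plans a listing of all AEs, SAP 8.2 shows dates there as reported, and a Data Evaluation Meeting precedes unblinding (5.1.3). That stands too. However, the imputed date is not shown, so a reader of the listing would not see why the event is missing from the tables.

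Three stronger readings might be inferred, and the documents do not support them:

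- **That events known to be on treatment are removed.** The true onset is unknown by construction. These are events that could have started on treatment, which is the situation the conservative principle is written for.
- **That 73% of partially dated AEs are lost, or that every year-only event is.** The figure is conditional on the four conditions and the assumed dates. In 27.1% of the enumerated cases the event remains a TEAE, and it always does when no Period 2 dose was given. The plan assumes 25% dropout (SAP 3).
- **That the day-missing rule also removes rozanolixizumab events.** It reaches only events that ended during Run-In, when everyone receives placebo.

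**Conclusion.** The inconsistency is real and follows from the text alone: the year-only fallback contradicts both the principle and the priority order stated in the same section. Under the conditions listed, the error runs in one direction, away from counting a possible on-treatment event.

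Its size can be given only conditionally: 72.9% against 0%, assuming a year-only start, onset in Period 1, an end before Period 2, a Period 2 dose received, a full Screening period and evenly spread start dates. The number of such AEs is not stated and is probably very small. With about 20 participants in Sequence 1, one participant whose only TEAE in a category was reclassified would change that incidence by 1/20, or 5 percentage points. The efficacy analyses are untouched. This is a defect in a rarely used derivation that is worth correcting because correction is cheap; it does not show that the safety tables will mislead.

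**What to change.** In SAP 8.2.1, replace the closing sentence of both partial-date cases. When the imputed start is after a known end date, try the Period 1 first-dose date and then the Run-In first-dose date. Accept each only if it agrees with the known year (and month, where known) and is on or before the end date. Use the 1st of the month, 1 January or Screening only if neither fits.

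Use the same on-or-before comparison in the unknown-date case, which now requires a date strictly before the end. Otherwise the three cases would still disagree for an event ending on a first-dose day.

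The cost is a few sentences in SAP 8.2.1 and one derivation in the AE dataset program, with no new data. A query for AEs with partial start dates and an early known end would show at once whether any event changes class.

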### Calculation rules for AE duration

Data availability	Onset date	Outcome date	Calculation rules
Complete data	D1	D2	Duration = D2 – D1 +1 day
Start date partially or completely missing	--	D2	Duration = D2 – D0 +1 day Notes: D0 is imputed start date per above rules.
End date partially missing or completely missing	D1	--	For ongoing AE: Duration = >Discharge date – D1 For resolved AE: Duration = < Discharge date – D1 Where discharge refers to the date of the SFU/EOS visit, or the date of last contact if the participant did not attend the SFU/EOS visit.

